5.5.1. Procedures for Subject Follow-up

Subjects who permanently discontinue randomized treatment will be asked to attend an Early Treatment Discontinuation visit and will be expected to attend in-clinic study visits

through to Follow-up according to the study visit schedule, unless consent is actively withdrawn. Complete details are provided in [Table 7](#) in Section 7.1.

- Early Treatment Discontinuation visit: This visit should occur within 2 weeks of the last dose of randomized treatment.
- Remaining in-clinic visits*:
 - Day 1 through Week 52: Study visits every 12 weeks \pm 2 weeks post Early Treatment Discontinuation visit.
 - Follow-up: Study visit 4 weeks after Week 52.

*Phone visit acceptable in exceptional circumstances.

- In all cases, reasons for Early Treatment Discontinuation and the date of last dose will be recorded.
- If a subject does not agree to continue attending in-clinic or phone visits, other follow-up options to collect study outcomes and vital status should be pursued according to local laws and regulations. If one of these alternate methods to collect study outcomes and vital status is acceptable to the subject, then the subject will be considered to have remained in the study and not to have withdrawn consent.

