9. STATISTICAL CONSIDERATIONS AND DATA ANALYSES

9.1. Primary Hypotheses

The primary Hgb efficacy objective will assess the estimand defined as the comparative treatment effect in mean Hgb change between baseline and EP (i.e., Weeks 28 to 52 inclusive) in all randomized subjects; defined as those who remain in follow-up throughout the period of stabilization and have at least one Hgb assessment during the EP (i.e., Weeks 28 to 52) regardless of adherence to study treatment. The analysis will test whether daprodustat is non-inferior to rhEPO according to the following statistical hypotheses:

- **Null:** The difference in mean change in Hgb between baseline and EP, between treatment arms (daprodustat-rhEPO), is less than or equal to -0.75 g/dL.
- **Alternative:** The difference in mean change in Hgb between baseline and EP, between treatment arms (daprodustat-rhEPO), is greater than -0.75 g/dL

The non-inferiority margin is pre-defined as -0.75 g/dL; selected to be consistent across all clinical trials in the daprodustat Phase 3 clinical development program in subjects with anemia of chronic kidney disease, and determined based upon a combination of clinical judgment, statistical reasoning and regulatory guidance for designing non-inferiority trials.

Statistical significance of non-inferiority will be assessed at the one-sided 2.5% level. An analysis of covariance (ANCOVA) model including randomization stratification factors, baseline hemoglobin and treatment will be used to obtain a point estimate and the two-sided 95% CI for the treatment difference (daprodustat-rhEPO) and generate the p-value for the non-inferiority test. The non-inferiority p-value will show strength of evidence against the null hypothesis. Non-inferiority will be established if the lower limit of the two-sided 95% CI for the treatment difference is greater than -0.75 g/dL.

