9.2. Sample Size Considerations

9.2.1. Sample Size Assumptions

The size of this study has been determined to be sufficient to meet the ICH E1 guideline for subject exposure, number and duration and to provide at least 90% power to test the primary non-inferiority hypothesis with a two-sided 95% CI.

Approximately 300 subjects are planned to be randomized (150 per arm) to receive daprodustat or rhEPO, to provide at least 100 subjects exposed to daprodustat for one year. Subjects will be treated to achieve and maintain Hgb between 10 and 11 g/dL. The expected difference in mean Hgb change from baseline and the EP, between arms, is 0 g/dL and the anticipated between subject standard deviation (SD) is 1.5 g/dL, based on historical rhEPO trials and daprodustat clinical trial experience to date. With a pre-specified non-inferiority margin of -0.75 g/dL, a two-sample T-test and assuming that up to approximately 30% of subjects will permanently stop randomized treatment before Week 28 (start of EP), 300 randomized subjects will provide >90% power to test the primary hypothesis.

With 300 randomized subjects, it is anticipated that the difference in mean Hgb change from baseline between arms will be estimated with a precision of 0.408 g/dL (half width of the two-sided 95% CI) and the largest (most negative) difference between arms that would meet the statistical criterion for non-inferiority would be -0.342 g/dL.

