7.1.2.5. Statistical Analyses/Methods

Primary Hgb Efficacy Statistical Analyses
Endpoint(s)

 • Mean change in Hgb between baseline and EP
Model Specification

 • Hgb during the EP will be defined as the mean of all available post-randomization Hgb values (on and off-treatment) during the EP (Week 28-52). • The ANCOVA model used to quantify the difference in mean Hgb change will adjust for the following baseline values: 
 ○ Treatment ○ Baseline Hgb (see Section 10.5.2) ○ Dialysis type (as randomized, see Section 0) ○ Dialysis start manner (whether dialysis start is planned or unplanned; as randomized)
Multiple Imputation Analysis

 • Multiple imputation analysis will be performed using all available Hgb values (on and off-treatment) and conducted under a set of assumptions about missing Hgb values (see Section 10.6.3). 
 ○ Intermittent missing post-baseline scheduled Hgb data in both arms through Week 52 will be imputed using PROC MI procedure with NIMPUTE = 200 and MCMC IMPUTE = monotone to generate 200 datasets with only monotone missing patterns. Burn in iterations (NBITER) and maximum iteration (MAXITER) will both be set to 500. The seed for reproducibility is set to 201410. The imputations will be done by randomized treatment, dialysis type, and dialysis starting manner. ○ For each of the monotone missing dataset (out of the 200 imputed as indicated above), the missing scheduled Hgb values through Week 52 will be imputed based on the MAR assumption and will be performed using PROC MI by treatment, dialysis type, and dialysis start manner. The monotone regression will have baseline Hgb, prior scheduled (possibly imputed) Hgb values, and may include dialysis type and dialysis start manner, as covariates (see Model Checking & Diagnostics, below). The seed for reproducibility is set to 201410. ○ The low and high cutoffs at Hgb values of 6 g/dL and 15 g/dL will be applied to all imputed Hgb values. ○ EP Hgb values will be computed and compared across treatment groups using the co-primary ANCOVA model described above. Rubin's rules [Rubin, 1987] will be used to combine results of the imputed datasets using SAS PROC MIANALYZE procedure. As a result, a single estimated treatment difference and its standard error will be produced, with which a 95% CI will be calculated.

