- The number and percentage of subjects with imputed data in the primary Hgb analysis will be provided by treatment group. The number and percentage of subjects by reason for data imputation will be provided. Reasons include: intermittent missing Hgb values, death before Week 28, death during Week 28 – 52, investigator site closed before Week 28, investigator site closed during Weeks 28-52, lost to follow-up before Week 28, lost to follow-up during Week 28 – 52, consent withdrawn before Week 28, consent withdrawn during Week 28 – 52, and other monotone missing Hgb values. Subjects will be further classified as either having observed all 7 scheduled EP Hgb values, having observed a partial schedule of EP Hgb values, having observed no scheduled EP Hgb values with at least one unscheduled EP Hgb value, or having observed no EP Hgb values, scheduled or unscheduled. For subjects with partial scheduled EP Hgb values, both the pattern of imputed data (intermittent, monotone) and the amount of imputed data (1 – 6 scheduled Hgb values missing) will be summarized. For subjects with partial scheduled EP Hgb values and a monotone imputed data pattern, the reason for the monotone imputed scheduled EP Hgb values will be provided. Reasons include: death during Week 28-52, investigator site closed during Weeks 28-52, lost to follow-up during Week 28 – 52, consent withdrawn during Week 28 – 52, and other monotone imputed Hgb values. And for summaries of the amount of missing scheduled EP Hgb values, the presence or absence of additional unscheduled EP Hgb values will be summarized.
- The least square (LS) mean estimates and standard errors by treatment group, LS mean difference, two-sided 95% CI and one-sided non-inferiority p-value for the difference in the primary Hgb endpoint between the daprodustat and darbepoetin alfa arms from the ANCOVA model will be presented. The number of subjects contributing to the analysis and the associated mean and standard deviation of the baseline and EP Hgb values will also be displayed with the results of the ANCOVA model.
- The LS mean difference, and associated two-sided 95% CI will be displayed on a forest plot together with supportive analysis results (excluding the Tipping Point Analysis).

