10.3. Appendix 3: Assessment Windows

10.3.1. Assessment Windows

Data for continuous variables that are not related to time-to-event will be summarized according to the scheduled visit time period for which they were recorded in the eCRF. Unscheduled assessments will not be slotted to a particular time point, but will remain as unscheduled if they are either summarized or listed unless otherwise specified (i.e. Hgb endpoints described in Section [10.6.3](#) and BP endpoints described in Section [10.6.4](#)).

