10.6.3. Efficacy

10.6.3.1. Hemoglobin Endpoints

Hemoglobin Values
Central Laboratory and HemoCue Hgb Values

 When source of Hgb measurement is not specified: 
 For reporting purposes, central laboratory Hgb values will be used, unless otherwise specified. However, if a central laboratory Hgb value is missing, a corresponding non-missing HemoCue Hgb value will be used. This approach will be used for the primary Hgb analysis. Some displays may be created for either central laboratory Hgb values only or HemoCue Hgb values only. The central laboratory summary will be considered the primary summary in this case.
Evaluable Hemoglobin Values

 Evaluable Hgb values are on-treatment Hgb values (see Section 10.4.1.1) that are not taken within the 8 weeks following a red blood cell transfusion, a whole blood transfusion, or a non-randomized ESA treatment which occurs on or after the randomization date. Red blood cell transfusions, whole blood transfusions and non-randomized ESA treatments occurring on or after the randomization date are identified by comparing the start and stop date of the respective transfusion or ESA concomitant medication record to the randomization date.
Imputed Hemoglobin Values

 For each missing value between baseline to Week 52 (inclusive), 200 imputed values will be generated using the multiple imputation method (see Section 7.1.2). The average of these 200 imputed values will be used as the value for this missing value in the summary tables and figures. For the primary efficacy Hgb analysis and the corresponding subgroup analyses using all available observed and imputed Hgb values (on and off-treatment), Rubin's rules [Rubin, 1987] will be used to combine results of the imputed datasets using SAS PROC MIANALYZE procedure.
EP Hemoglobin Value for Primary Hgb Analysis

 For each subject, the mean of all available (on and off treatment) Hgb values during the EP (See Section 10.6.1) including any imputed and unscheduled Hgb values that were taken during this time period. Should the assessment dates for Hgb values from the Early Treatment Discontinuation visit fall within the EP, then these values will be included as unscheduled Hgb values. Hgb values from the Follow-up visit will not be included in the EP mean.

CONFIDENTIAL

201410

Hemoglobin Values					

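### An Hgb recorded as unscheduled neither fills nor informs a missed scheduled visit; the primary analysis imputes that visit and averages the imputation with the measurement

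*SAP*

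**What the plan says.** SAP 10.3.1 takes the visit label from the eCRF and adds that "Unscheduled assessments will not be slotted to a particular time point". The same sentence excepts the Hgb endpoints of Section 10.6.3, so the rule for the primary endpoint has to be read there and in 7.1.2.5.

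- **Imputation (SAP 7.1.2.5).** Missing scheduled Hgb is filled through Week 52, by arm and stratum: intermittent gaps first, then monotone ones. On predictors: "The monotone regression will have baseline Hgb, prior scheduled (possibly imputed) Hgb values"; the strata may be added as covariates. Unscheduled values are not listed.
- **EP mean (SAP 10.6.3.1).** The primary EP value averages everything in the period, "including any imputed and unscheduled Hgb values that were taken during this time period". Early Treatment Discontinuation values that fall in the EP are expressly treated as unscheduled.
- **Same-date table (SAP 10.6.3.1).** An unscheduled central laboratory value on the same date as a scheduled HemoCue value is the one used, and it is labelled unscheduled.
- **Reporting (SAP 7.1.2.5).** One class in the imputation summary is subjects "having observed no scheduled EP Hgb values with at least one unscheduled EP Hgb value".
- **Follow-up after stopping (Protocol 5.5.1).** "Study visits every 12 weeks", with a 2-week tolerance, counted from the Early Treatment Discontinuation visit.
- **Estimand (SAP 7.1.2.4).** Treatment discontinuation, non-randomized ESA, rescue and transfusion are all handled by treatment policy; only death is hypothetical.

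**The concern.** Under a treatment-policy estimand, Hgb measured after a subject stops treatment is the direct evidence for that subject's outcome. Under these rules, a measurement without a scheduled label enters the EP mean only as an extra value. The visit beside it is still imputed, from a model that has not seen the measurement and is not conditioned on being off treatment. The subject's score can then rest mainly on values predicted from others in the same arm, many of them still on treatment.

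The tipping-point analysis inherits the problem. It adds a growing multiple of delta from the first monotone-missing visit and leaves intermittent gaps alone. Suppose a subject was last seen on schedule at Week 12 and has unscheduled values near Weeks 24, 36 and 48. Every visit from Week 16 counts as monotone-missing, and Week 52 is shifted by (52 − 16)/4 + 1 = 10 deltas, subject to the 6 and 15 g/dL cutoffs. If the Week 48 value were recognised as a visit, only Week 52 would be monotone-missing, with 1 delta.

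The same-date row has this effect whatever label the 12-weekly visits carry: a scheduled visit can be left empty, and imputed, although Hgb was measured that day.

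**Working it through.** **The plan's own figures.** Protocol 9.1: "Statistical significance of non-inferiority will be assessed at the one-sided 2.5% level". Protocol 9.2.1 gives a "pre-specified non-inferiority margin of -0.75 g/dL", SD 1.5 g/dL, 150 per arm and up to about 30% stopping treatment before Week 28. On the assumed effect: "The expected difference in mean Hgb change from baseline and the EP, between arms, is 0 g/dL".

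- n = 150 × 0.70 = 105 per arm.
- Half width = t(0.975, 208) × 1.5 × √(2/105) = 0.408 g/dL, as stated.
- Most negative passing difference = −0.75 + 0.408 = −0.342 g/dL, as stated.
- Power = 95%, as in the Protocol 9.2.2 table.

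The documents give no figure for the weight of imputed values.

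**Weight of imputed values.** The EP has 7 scheduled visits (Weeks 28, 32, 36, 40, 44, 48, 52). Take a subject with none observed and k unscheduled EP values. As written, the imputed share is 7/(7 + k). With each value assigned to its own scheduled visit, it is (7 − k)/7.

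| k | As written | Assigned to visits |
|---|---|---|
| 1 | 7/8 = 88% | 6/7 = 86% |
| 2 | 7/9 = 78% | 5/7 = 71% |
| 3 | 7/10 = 70% | 4/7 = 57% |

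**Likely k, if the 12-weekly visits are recorded as unscheduled.** A simulation assumed stopping times uniform over the interval, a discontinuation visit within 2 weeks, later visits every 12 ± 2 weeks, and full attendance.

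- Stopping before Week 28: k = 2 in 88% of subjects; mean imputed share 78% as written, 72% assigned.
- Stopping during the EP: mean imputed share 41% as written, 31% assigned.

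**Error in the EP mean.** Let true off-treatment Hgb lie D below the imputed path. The EP mean is then too high by 7D/(7 + k), which is 0.78D at k = 2. With assignment, the measured values also act as predictors. For a subject on treatment to Week 20 with values assigned to Weeks 32 and 44, the error becomes:

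- 0.09D to 0.35D under AR(1) correlation of 0.9 to 0.5 (assumed);
- 0.51D to 0.54D under compound symmetry (assumed).

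**Arm-level shift** = p × 7/9 × D, where p is the proportion of the arm affected.

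- p = 30%, D = 0.5: 0.30 × 0.778 × 0.5 = 0.12 g/dL.
- p = 30%, D = 1.0: 0.30 × 0.778 × 1.0 = 0.23 g/dL.
- p = 20% to 40%, D = 0.5 to 1.0: 0.08 to 0.31 g/dL.

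The treatment difference moves by the gap between the two arms' shifts. At p = 30% in both arms, using up the whole 0.342 g/dL would need D to differ between arms by 0.342/(0.30 × 0.778) = 1.5 g/dL.

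**Part removed by assignment** at p = 30%, D = 0.5, k = 2:

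- AR(1): 0.30 × 0.5 × (0.778 − 0.349) = 0.06 to 0.30 × 0.5 × (0.778 − 0.093) = 0.10 g/dL.
- Compound symmetry: 0.30 × 0.5 × (0.778 − 0.536) = 0.04 g/dL, and the same to two decimals with 0.513.

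**The case against.** The strongest reply is that the 12-weekly visits may not be unscheduled at all. Both documents' tables for subjects off treatment give these visits a column separate from the unscheduled one, and SAP 10.6.3.1 singles out only the Early Treatment Discontinuation value as unscheduled. If the eCRF gives the visits nominal weeks, they fill those weeks and enter the imputation. The reporting class with only unscheduled EP values would also fit a subject whose one EP sample was ad hoc. This stands: the number affected cannot be read from the documents.

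It also stands that most of the imputed weight comes from 12-weekly follow-up against a 4-weekly grid, and that deaths and withdrawals leave no later value to assign. The 30% is an upper planning figure for stopping treatment, not a count of subjects who stop and then attend every visit.

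A reader might infer that the rule pulls the arms together and so favours non-inferiority. The documents do not support that. Imputation is done within arm, so it carries forward each arm's own pattern. If rescued subjects in both arms move to similar local care and their Hgb converges, within-arm imputation could instead hold the arms apart.

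Finally, SAP 7.1.2.5 already has a supportive ANCOVA on observed Hgb for the COVID assessment, a tabulation of imputation patterns, and a tipping-point analysis. These help a reader judge the result but leave the primary rule as it is, and the tipping-point analysis shares the defect.

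**Conclusion.** The point holds for any Hgb without a scheduled label: discontinuation-visit values, ad hoc samples, the same-date case, and the 12-weekly visits if the eCRF records them as unscheduled. Such a value neither fills nor predicts the missing visit. For a subject with no scheduled EP value, 70% to 88% of the EP mean is then imputed (k = 3 to 1).

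The arm-level shift of about 0.12 to 0.23 g/dL assumes that 30% of the arm is affected, k = 2, and D = 0.5 to 1.0 g/dL. None of these is documented for this purpose. The shift cancels if the arms are alike, its sign is not known in advance, and assignment to visits removes only part of it.

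Two stronger readings should be resisted. Measured values are not discarded; they enter the EP mean with reduced weight. Nor do imputations dominate the endpoint as a whole: that is true only of subjects missing most scheduled EP visits, and for stops during the EP the measured values keep the larger share on average. The change should be made because it is cheap and fits the estimand better, not because a bias of known size has been shown.

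**What to change.** Before unblinding, amend SAP 7.1.2.5 and 10.6.3.1 as follows.

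1. State how the 12-weekly visits after discontinuation are labelled in the eCRF. If they already carry nominal weeks, saying so closes most of the point.
2. Assign each dated post-randomization Hgb that is not already at a scheduled visit to the nearest empty scheduled visit within ±2 weeks. On a 4-weekly grid this window reaches every date in the EP.
3. Use the assigned values in the imputation models and impute only visits that remain empty. Apply the same data to the tipping-point analysis, so that delta is not added to a visit that now has a measurement.
4. Change the same-date row so that an unscheduled central laboratory value on the date of a scheduled HemoCue value counts as that scheduled visit.

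The cost is about one SAP paragraph, one changed table row and a windowing step in programming. The downside is a timing approximation of up to 2 weeks for assigned values.

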10.4. Appendix 4: Treatment States and Phases

10.4.1. Treatment Phases

Assessments and events will be classified according to the time of occurrence relative to treatment start and stop dates and last non-zero dose date (see Section 10.6.1).

10.4.1.1. Treatment States for Hgb, Iron Parameters, IV Iron Dose Endpoints, Iron Use Summaries, Transfusion and PRO Data

Treatment Phase	Definition
Pre-Treatment	Date ≤ Treatment Start Date
On-Treatment	Treatment Start Date < Date ≤ Treatment Stop Date + 1 day
Post-Treatment	Date > Treatment Stop Date + 1 day
Post-Randomization	Randomization Date < Date

NOTES:

If the treatment stop date is missing and the treatment start date is non-missing and Date > Treatment Start Date, then the assessment will be considered to be On-Treatment

10.4.1.2. Treatment States for CV Endpoint Data

Treatment State	Definition
Pre-Treatment	Date < Treatment Start Date
On-Treatment	Treatment Start Date ≤ Date ≤ Last Non-Zero Dose Date + 28 days
Post-Treatment	Date > Last Non-Zero Dose Date + 28 days
Post-Randomization	Randomization Date ≤ Date

NOTES:

- If the last non-zero dose date is missing and the treatment start date is non-missing and Date ≥ Treatment Start Date, then the assessment will be considered to be On-Treatment
- Treatment state definitions use the imputed CV endpoint date

10.4.1.3. Treatment States for BP, Lipid Parameters, Clinical Chemistry, Hematology, Other Laboratory Tests, Hepatobiliary (Liver) and Vital Signs Data

Treatment State	Definition
Pre-Treatment	Date ≤ Treatment Start Date
On-Treatment	Treatment Start Date < Date ≤ Last Non-Zero Dose Date + 1 day
Post-Treatment	Date > Last Non-Zero Dose Date + 1 day
Post-Randomization	Randomization Date < Date

NOTES:

- If the last non-zero dose date is missing and the treatment start date is non-missing and Date > treatment start date, then the assessment will be considered to be On-Treatment

10.4.1.4. Treatment States for AE Data

AEs are to be recorded on the eCRF from the start of randomization treatment until the Follow-up visit, at the timepoints specified in the Time and Events table from Section 10.2.1. Serious AEs assessed as related to study participation or related to a GSK product are to be reported on the eCRF from the time a subject consents to participate in the study

CONFIDENTIAL

201410

up to and including any follow-up contact. AE of worsening of an on-going event will be counted once in a particular treatment state.

Treatment State	Definition
Pre-Treatment	
 For subjects with a non-missing screen failure date, if AE onset is on or before the screen failure date: AE Start Date \leq Screen Failure Date For randomized subjects with a missing treatment start date, all AEs are considered pre-treatment For randomized subjects with a non-missing treatment start date, if AE onset date is before treatment start date: AE Start Date $<$ Treatment Start Date
Post-Randomization	
If AE onset date or AE worsening date is on or after the randomization date Randomization date \leq AE Start Date Randomization date \leq AE Worsening Date AE worsening during post-randomization will be defined relative to the maximum intensity of AE prior to randomization date.
 
AE worsening date is the first date in the post-randomization period, when AE intensity increased relative to the maximum intensity of the AE prior to randomization date.

Treatment emergent	
If AE onset date or AE worsening date is on or after treatment start date & on or before the last non-zero dose date plus 1 day. Treatment Start Date \leq AE Start Date \leq Last Non-Zero Dose Date + 1 day Treatment Start Date \leq AE Worsening Date \leq Last Non-Zero Dose Date + 1 day AE worsening during treatment emergent will be defined relative to the maximum intensity of AE prior to randomized treatment start date.
 
AE worsening date is the first date in the treatment emergent period, when AE intensity increased relative to the maximum intensity of the AE prior to randomized treatment start date.

Follow-up	
If AE onset date or AE worsening date is after the last non-zero dose date plus 1 day. AE Start Date $>$ Last Non-Zero Dose Date + 1 day AE Worsening Date $>$ Last Non-Zero Dose Date + 1 day AE worsening during follow-up will be defined relative to the maximum intensity of AE prior to randomized treatment start date.
 
AE worsening date is the first date in the follow-up period, when AE intensity increased relative to the maximum intensity of the AE prior to randomized treatment start date.

Onset /Worsening Time Since 1 st Dose (Days)	
If Treatment Start Date $>$ AE Onset Date: AE Onset Date - Treatment Start Date If Treatment Start Date \leq AE Onset Date: AE Onset Date - Treatment Start Date + 1 If Treatment Start Date $>$ AE Worsening Date: AE Worsening Date - Treatment Start Date If Treatment Start Date \leq AE Worsening Date: AE Worsening Date - Treatment Start Date + 1 Missing otherwise.

Onset /Worsening Time Since Last Dose (Days)	
If Last Non-Zero Dose Date \leq AE onset date: AE onset date – last non-zero dose date + 1 If Last Non-Zero Dose Date $>$ AE onset date: AE onset date – last non-zero dose date

CONFIDENTIAL

201410

Treatment State	Definition
	If Last Non-Zero Dose Date \leq AE worsening date: AE worsening date – last non-zero dose date + 1 If Last Non-Zero Dose Date $>$ AE worsening date: AE worsening date – last non-zero dose date Missing otherwise.
Duration (Days)	AE Resolution Date – AE Onset Date/AE Worsening Date + 1
Drug-related	If relationship is marked 'YES' on eCRF or if the value is missing.

NOTES:

- AEs that occur or worsen during interruptions of randomized study treatment will be classified as treatment emergent and post-randomization.
- If the last non-zero dose date is missing and the treatment start date is non-missing and the AE onset date or AE worsening date is on or after the treatment start date, then the AE will be considered to be treatment emergent.
- If AE onset date or AE worsening date is missing and AE resolution date is before the treatment start date, then the AE will be classified as Pre-treatment.
- If AE onset date or AE worsening date is missing and AE resolution date is either missing or on or after treatment start date, then the AE will be classified as treatment emergent and post-randomization.

10.4.1.5. Treatment States for Concomitant Medications (Other Than IV Iron Dose Endpoints and Iron Use Summaries)

Pre-treatment medications are those taken (i.e., started) before the start date of randomized treatment. On-treatment medications are those taken (i.e., started or continued) at any time between the randomized treatment start date and the last non-zero dose date + 1 day, inclusive. Pre-treatment medications that were continued during this on-treatment period are also considered to be on-treatment medications. Post-treatment medications are those taken (i.e., started or continued) at any time after the last non-zero dose date + 1 day. On-treatment medications that were continued during this post-treatment period are also considered to be post-treatment medications. Post-randomization medications are those taken (i.e., started or continued) at any time on or after the randomization date.

It will be assumed that the medication has been taken on the date in which it is reported as started or stopped. Also, for any medication starting on the same date as randomized treatment, it will be assumed that the medication was taken after the subject started taking randomized treatment.

Illustrations of the pre-treatment, on-treatment, and post-treatment treatment states are included below:

CONFIDENTIAL

201410

	Pre-treatment	On-treatment			Post-treatment	Pre-treatment medication	On-treatment medication	Post-treatment medication
		Randomized Treatment Start Date	Last Non-zero Dose Date + 1 Day	Last Non-zero Dose Date + 2 Days				
(a)	x—x					Y	N	N
(b)	x—		—x			Y	Y	N
(c)	x—		—	—x		Y	Y	Y
(d)		x—x				N	Y	N
(e)		x—			—x	N	Y	Y
(f)					x—x	N	N	Y
(g)	?—x					Y	N	N
(h)	?—		—x			Y*	Y	N
(i)	?—		—		—x	Y*	Y*	Y
(j)	x—		—		—?	Y	Y**	Y**
(k)		x—			—?	N	Y	Y**
(l)					x—?	N	N	Y
(m)	?—		—		—?	Y***	Y***	Y***
(n)	x—	x				Y	Y	N
(o)	?—	x				Y*	Y	N
(p)		x	—x			N	Y	N
(q)		x	—	x		N	Y	N
(r)				x	—x	N	Y	Y
(s)				x	—?	N	Y	Y**
(t)				x	—x	N	N	Y
(u)				x	—?	N	N	Y
(v)		x—	—	x		N	Y	Y

x = start/stop date of medication

? = missing start/stop date of medication

* If a medication is stopped On-treatment or Post-treatment and no start date is recorded it will be assumed that the medication was ongoing from the Pre-treatment phase

** If a medication is started Pre-treatment or On-treatment and no stop date is recorded then usage will be assumed to be ongoing for the remainder of the study

*** If a medication has no start or stop date it will be assumed that the medication was ongoing from the Pre-treatment phase to the Post-treatment phase

CONFIDENTIAL

201410

